2.2. Endpoints

Primary endpoint:

1. Percentage of Eyes with slit-lamp findings (Grade 3 or 4) related to study lens wear

Slit Lamp Findings (Grade 3 or higher) will be assessed for each subject eye at all study visits (scheduled and unscheduled). However, the primary endpoint will be the percentage of eyes with Grade 3 or higher SLFs related to study lens wear, after approximately 2 weeks of lens wear.

SLFs will be evaluated and classified using the FDA Grading scale rating from 0 to 4, where Grade 0 represents the absence of findings and 1 to 4 representing successively worse findings (i.e., Grade 1=trace, Grade 2= mild, Grade 3=moderate and Grade 4= severe).

Exploratory Endpoints:

1. Distance Monocular HLHC logMAR Visual Acuity

Visual acuity (VA) will be assessed monocularly at the 1-week follow-up visits under high-luminance high contrast (HLHC) conditions at a test distance of 4 meters using ETDRS Charts. The logMAR VA score is a continuous endpoint.

2. CLUE Comfort Scores

Subjective comfort will be assessed using the Contact Lens User Experience (CLUE) questionnaire. CLUE will be assessed at the fitting, 1- and 2-week follow-up visits. The CLUE comfort score is a conintuous endpoint.

CLUE is a validated patient-reported outcomes questionnaire to assess patient-experience attributes of soft, disposable contact lenses (comfort, vision, handling, and packaging) in a contact-lens wearing population in the US, ages 18-65. Derived CLUETM scores using Item Response Theory (IRT) follow a normal distribution with a population average score of 60 (SD 20), where higher scores indicate a more favorable/positive response with a range of 0-120. A 5-point increase in an average CLUETM score translates into 10% shift in the distribution of scores for population of soft contact lens wearers.⁵

- 3. CLUE Vision Scores at the fitting, 1-, and 2-week follow-up visits. The CLUE vision score is a conintuous endpoint.
- 4. CLUE Handling Scores at the fitting, 1-, and 2-week follow-up visits. The CLUE handling score is a conintuous endpoint.

CR-6553, v3.0 JJVC CONFIDENTIAL

5. Toric Lens Orientation

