14.7. Exploratory Analyses

Summary for exploratory endpoints will be provided for both the ITT and the Per-Protocol populations. However, all analyses for exploratory endpoints will be conducted on the ITT population.

Distance Monocular HLHC logMAR visual acuity

Distance monocular HLHC logMAR visual acuity at the 1-week follow-up will be summaried and presented only descriptively by lens type accompanied with the 2-sided 95% CIs. Summary statistics are described in section 14.1.

CLUE Comfort, Vision, and Handling Scores

The analysis of exploratory endpoints of CLUE comfort, vision and handling at the fitting, 1-, and 2-week follow-up visits will be conducted separately for each CLUE domain. The exploratory analysis of each CLUE score endpoints will include the estimation of mean CLUE scores and associated 95% CIs for each study lens (Test lens and Control lens). Additionally, the mean difference between the Test and Control lens paired with the 95% CI will be calculated.

CLUE scores will be analyzed using a linear mixed model, adjusting for baseline scores as a covariate. Sequence of lens wear, study period, lens type (Test and Control), timepoint (fitting, 1-week, and 2-week follow-up visit), and the ineraction lens type by timepoint will be included as fixed effects. Other baseline characteristics such age, gender, and/or race will be included as fixed covariates when appropriate. Site and subject nested within site will be included as random effects (G-side). Residual errors from measurements within the same subject and timepoint across study period will be modeled using an unstructured covariance structure (UN). If the model does not converge, other covariance structures will be considered. The Kenward and Roger method will be used for the denominator degree of freedom. Estimates for each study lens and between study lenses (Test lens and Control lens) will be carried out using two-sided 95% CIs for the least-square mean and/or mean difference.

Toric Lens Orientation

The distribution (counts, percentages) of eyes for the toric Orientation (in degrees) at 1- and 3-minutes after lens insertion will be summarized by timepoint (fitting, 1-, and 2-week follow-up) and lens type.

Mean Settled Lens Orientation

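### The CLUE model treats the Test-Control differences at the three visits as uncorrelated, so a difference averaged over visits would get too narrow a CI if lens preference persists

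*Combined protocol and SAP*

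**What the plan says.** Section 14.7 describes one linear mixed model per CLUE domain.

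- **Fixed effects.** Baseline score, sequence, period and lens type, together with "timepoint (fitting, 1-week, and 2-week follow-up visit), and the ineraction lens type by timepoint will be included as fixed effects".
- **Random effects.** "Site and subject nested within site will be included as random effects (G-side"). There is no subject-by-period term. In a 2×2 crossover, that would be the same as a subject-by-lens term.
- **Residuals.** "Residual errors from measurements within the same subject and timepoint across study period will be modeled using an unstructured covariance structure (UN"). The block is one subject at one timepoint and holds that subject's two period scores.
- **Fallback.** "If the model does not converge, other covariance structures will be considered". The alternatives are not named.
- **Degrees of freedom.** "The Kenward and Roger method will be used for the denominator degree of freedom". No robust variance is planned.
- **Output.** After the means for each lens: "Additionally, the mean difference between the Test and Control lens paired with the 95% CI will be calculated". The closing sentence reads in part: "Estimates for each study lens and between study lenses (Test lens and Control lens) will be carried out using two-sided 95% CIs". Neither sentence says whether the contrast is taken at each visit or over all visits.

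The objectives in section 2.1 and the endpoint definitions in section 2.2 list CLUE at the fitting, 1-week and 2-week visits.

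**The concern.** Each subject gives six scores per domain: three visits in each of two periods. Three of them concern the same lens, fitted once and then worn at the same code and power (section 7.2, step 2.13). A subject who finds one lens more comfortable will probably say so at all three visits. The written model has no term for this. Its subject effect raises or lowers all six scores together, whichever lens is worn.

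The residual block also carries nothing that lets variance change with time. The fitting questionnaire asks about initial impressions (step 1.24), while the later ones follow days of wear, so equal spread is not assured.

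At stake is the stated precision of the CLUE lens differences. Sections 2.3 and 14.4 rule out hypothesis tests, so the estimates and their intervals are what a reader will use to compare the lenses.

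**Working it through.** The plan gives no CLUE precision figure, so there is none to reproduce.

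**Inputs from the document.** n = 60 completers (section 14.2); two-sided 95% intervals (section 14.7); CLUE scores "follow a normal distribution with a population average score of 60 (SD 20") (section 2.2).

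**Assumed inputs.** The documents give neither the between-visit correlation of the lens difference, ρ, nor SDs by visit. For SEs in CLUE points, the variance of 20² = 400 was split into subject 180, subject-by-visit 20 and within-subject 200.

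**Step 1: what the model implies.** Let D_t be a subject's Test-Control difference at visit t. Under the written structure, two scores at different visits have covariance σ² (subject plus site), whether they concern the same lens or different lenses. Hence, for two different visits t and t′,

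Cov(D_t, D_t′) = σ² − σ² − σ² + σ² = 0.

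The three differences are taken as uncorrelated, with one variance V_D if the same 2×2 matrix serves all timepoints.

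**Step 2: difference averaged over visits.**

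- Model SE = √(V_D / 3n)
- True SE = √(V_D(1 + 2ρ) / 3n)
- Ratio = 1/√(1 + 2ρ); coverage ≈ 2Φ(1.96 × ratio) − 1

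| ρ | Ratio | Coverage |
|---|---|---|
| 0 | 1.00 | 95% |
| 0.3 | 1/√1.6 = 0.79 | 88% |
| 0.5 | 1/√2.0 = 0.71 | 83% |
| 0.7 | 1/√2.4 = 0.65 | 79% |

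The ratio does not depend on V_D.

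In CLUE points, V_D = 2 × 200 = 400, so the model SE is √(400/180) = 1.49 and the half-width is 2.94 (t = 1.974 on 170 df), whatever ρ is. A covariance that carries ρ gives half-widths of 2.98 / 3.65 / 4.22 / 4.72 at ρ = 0 / 0.25 / 0.5 / 0.75 (t on 58 df).

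**Step 3: check by simulation.** The written model was fitted by REML to 300 simulated trials of 60 subjects per scenario. The site variance was set to 0 because it cancels, and t on 170 df stood in for Kenward-Roger. Coverage for the visit-averaged difference at ρ = 0 / 0.25 / 0.5 / 0.75 was 97% / 89% / 85% / 79%; the formula with t = 1.974 gives 95% / 89% / 84% / 79%. By-visit coverage with equal spread was 92% to 97% throughout.

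**Step 4: by-visit differences with unequal spread.** Suppose the SD of the lens difference changes in proportion to the SD of the scores. The pooled SD is then used at every visit.

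- SDs 18/20/22: pooled √((324 + 400 + 484)/3) = 20.07. At 2 weeks the ratio is 20.07/22 = 0.91, coverage 93%. At fitting it is 20.07/18 = 1.11, coverage 97%.
- SDs 16/20/24: pooled √((256 + 400 + 576)/3) = 20.26. At 2 weeks the ratio is 20.26/24 = 0.84, coverage 90%. At fitting it is 20.26/16 = 1.27, coverage 99%.
- Equal SDs: ratio 1.00 at every visit.

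A simulation with within-subject residual variances of 100/200/300 and ρ = 0 gave coverage of 99% / 95% / 88%. With the order reversed it gave 89% / 97% / 100%, so the visit with the larger spread is the one under-covered.

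**Step 5: do the planned safeguards help?** Kenward-Roger adjusts for estimating the covariance parameters but takes the structure as correct. The fallback applies only if the fit fails to converge, and this model can converge while misspecified.

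**The case against.** The strongest reply is that by-visit differences are the intended target. Sections 2.1 and 2.2 tie CLUE to three named visits, and lens type by timepoint is in the model, which is what produces by-visit contrasts. Nowhere does the plan speak of averaging over visits. On that reading, with equal spread, the intervals are sound. This stands as far as it goes: the documents point at least as much to by-visit differences as to an overall one. But section 14.7 leaves the contrast open, and an overall lens difference is a natural product of this model.

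Three further replies have weight.

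- A reader might infer that the model leaves out all correlation between visits on the same lens. It does not. The subject effect correlates every pair of a subject's visits; only the additional, lens-specific part is absent.
- Unequal spread is an assumption. The documents give one population SD and no sign that spread grows with wear. The text also does not exclude a separate matrix for each timepoint. Section 14.1 has SDs reported by event and lens, so a change in spread would be visible afterwards, although the planned intervals would not be corrected for it.
- CLUE is exploratory, with no test, margin or decision rule attached, and point estimates and descriptive summaries are reported beside the intervals.

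**Conclusion.** The point holds conditionally. As written, the model treats the three lens differences as uncorrelated. The CI for a visit-averaged difference is then too narrow if two things are true: such a difference is reported, and ρ is above 0. Positive ρ is the expected direction for repeated ratings of one lens by one person, but the documents give no value. Over an assumed range of 0.3 to 0.7, coverage falls to between 88% and 79%; at ρ = 0 nothing is lost.

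A reader might go further and conclude that the overall interval is certainly too narrow, or that every CLUE interval is wrong. The documents support neither. By-visit intervals are correct with equal spread, and under the assumed unequal SDs they miss by a few percentage points.

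The primary slit-lamp endpoint and the sample size do not depend on this model. Priority: minor to moderate.

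**What to change.** In section 14.7:

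1. Add a random subject-by-period effect to the CLUE model and let the residual variance differ by timepoint. Alternatively, model all six scores in one subject-level covariance block that replaces the random subject effect, and name the subject-by-period version as the convergence fallback.
2. State whether the Test-Control difference is reported by visit, overall, or both. If by visit only, the between-visit correlation no longer affects the reported intervals, and only the common-variance question remains.

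The change is to wording and needs no new data or subjects. It costs a few more covariance parameters (the subject-by-period effect adds one; a fully unstructured six-score block has 6 × 7/2 = 21), some convergence risk with about 60 subjects, and a wider interval for any overall difference. At ρ = 0.5 under the assumptions above, the half-width would go from 2.94 to 4.22 CLUE points.

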2. STUDY OBJECTIVES, ENDPOINTS AND HYPOTHESES

2.1. Objectives

Primary Objective:

The primary objective of this study is to estimate the incidence rate (percentage) of eyes with clinically significant slit-lamp findings (Grade 3 or 4) related to each study lens (Test lens and Control lens) after approximately 2-weeks of lens wear.

Exploratory Objectives:

The exploratory objectives of this study include the estimation of the mean difference between study lenses (Test lens and Control lens) with respect to distance monocular high luminance, high contrast (HLHC), logMAR visual acuity (at the 1-week follow-up visit), and CLUE comfort, vision, and handling scores (at the fitting, 1- and 2-week follow-up visits). Additional exploratory objectives of the study are to estimate the mean and standard deviation of the settled toric roation of each study lens (Test lens and Control lens) following lens settling and after 1- and 2-weeks of lens wear, and to assess the toric lens orientation of each study lens, 1- and 3-minutes after lens insertion. Adverse events will also be monitored and collected.

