4. STUDY DESIGN AND RATIONALE

4.1. Description of Study Design

This will be a mulit-site, 6-visit, randomized, controlled, double-masked, bilateral wear, dispensing 2×2 crossover study.

At the initial visit (Visit 1), if a subject is deemed eligible, the subject will be randomized into one of two unique sequences of lens wear (Test/Control or Control/Test), otherwise, the subject will be deemed ineligible and exited from the study.

CR-6553, v3.0 JJVC CONFIDENTIAL

Subjects will wear each study lens (Test lens and Control lens) in a daily wear, daily disposable modality for approximately 2 weeks. There will be a washout period of 7±2 days between wear periods. Subjects will not have access to the study lenses following completion of the protocol.

Subjects will be advised to wear the study lenses for a minimum of 8 hours per day for at least 5 days during each wear period. Unscheduled visits may be conducted, if appropriate, and lost or damaged lenses may be replaced when necessary.

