4.2. Study Design Rationale

A 6-visit, double-masked, 2×2 crossover study design was chosen to demonstrate the study objectives. In this design, each subject will act as their own control to reduce the influence of potential confounding factors such as age, gender, race, and vision correction. To help further reduce the potential for carryover effects, a washout period of approximately 1-week (7 ± 2 days) between study will be used.

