5. TEST ARTICLE ALLOCATION AND MASKING

5.1. Test Article Allocation

The study lenses will be worn bilaterally in a randomized fashion using a 2×2 crossover design with 2 lens types and 2 periods.

A computer-generated randomization scheme will be used to randomly assign subjects to one of two unique sequences of lens wear. The randomization scheme will be provided by an internal independent unmasked Biostatistician who is independent of the study team and not involved in the study conduct or analyses, beyond the randomization codes and schedule generation. The randomization scheme will be generated using the PROC PLAN procedure from Statistical Analysis System (SAS) Software Version 9.4 or higher (SAS Institute, Cary, NC).

The assignment of subjects will be performed at the first visit prior to the first fitting. Clinical sites must follow the randomization scheme provided. The following must have occurred prior to randomization:

- Informed consent must have been obtained
- The subject must have met all inclusion and exclusion criteria
- The subject history and baseline information must have been collected

When dispensing test articles, the following steps should be followed to maintain randomization codes:

- 1. Investigator or designee (documented on the Delegation Log) will consult the randomization scheme (lens fitting schedule) to obtain the test article assignment for that subject prior to dispensing.
- 2. Investigator or designee will record the subject's number on the appropriate line of the randomization scheme (lens fitting schedule).
- 3. Investigator or designee will pull the appropriate test articles from the study supply. All test articles that are opened, whether dispensed (placed/fit on eye or dispensed outside the clinical site) or not, must be recorded on the Test Article Accountability Log in the "Dispensed" section.

CR-6553, v3.0 JJVC CONFIDENTIAL

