Mean settled lens orientation will be summarized separately for each timepoint (fitting, 1-, and 2-week follow-up visits) and lens type (Test and Control). Mean settled lens orientation is calculated by eye by averaging across all lens orientation measurements collected at least 15-minutes after lens insertion. The standard deviation of average settled lens orientation will also be calculated.

The exploratory analysis of this exploratory endpoint will include the estimation of the mean settled rotation by study lens paired with the corresponding two-sided 95% CIs for each lens, and the point estimate with the two-sided 95% CI for the mean difference.

Mean settled rotation will be analyzed using a linear mixed model. Sequence of lens wear, period, lens type, and first order carryover effect will be included in the model as fixed effects. Other baseline characteristics may be included, such as, race and age. Subject will be included as a random effect. Residual errors between measurements within a subject across periods will be modeled using an unstructured (UN) covariance structure. The Kenward and Roger Method will be used for the calculation of denominator degrees of freedom. Estimates will be calculated using two-sided 95% confidence intervals constructed for the least-square mean and/or least-square mean difference.

Adverse Events

All Adverse Events reported during this study will be provided in a listing. This listing will include subject demographic information, treatment information (associated with the time of the reported AE), AE type (ocular or non-ocular), seriousness / classification, causality or relatedness, adverse event severity, outcome, actions taken and the associated start and end date / time for each AE.

Additional exploratory analyses may be considered at the discretion of the study sponsor.

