14.10. Procedure for Reporting Deviations from Statistical Plan

The analysis will be conducted according to that specified in above sections. There are no known reasons for which it is planned to deviate from these analysis methods. If for any reason a change is made, the change will be documented in the study report along with a justification for the change.

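### The settled-rotation model fits sequence, lens type and first-order carryover together in a 2×2 crossover, so the Test−Control difference and its 95% CI cannot be estimated as written

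*Combined protocol and SAP*

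**What the plan says.** Section 4.1 sets the design: "the subject will be randomized into one of two unique sequences of lens wear (Test/Control or Control/Test"). Section 5.1 confirms the allocation as "using a 2×2 crossover design with 2 lens types and 2 periods".

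For mean settled lens orientation, section 14.7 specifies a linear mixed model: "Sequence of lens wear, period, lens type, and first order carryover effect will be included in the model as fixed effects". Subject is a random effect, the residual covariance across periods is unstructured, Kenward-Roger degrees of freedom are used, and baseline characteristics such as race and age may be added. From this model the plan promises a mean with 95% CI for each lens and "the point estimate with the two-sided 95% CI for the mean difference", through least-squares means. It gives no condition under which carryover would be removed and no fallback model.

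The CLUE model in the same section is different. Its fixed effects begin "Sequence of lens wear, study period, lens type (Test and Control), timepoint (fitting, 1-week, and 2-week follow-up visit") and add the lens-by-timepoint interaction. It has no carryover term.

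On carryover itself, section 4.2 relies on the washout: "To help further reduce the potential for carryover effects, a washout period of approximately 1-week".

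**The concern.** In a two-sequence, two-period, two-treatment crossover, first-order carryover is completely confounded with a combination of sequence and lens. A model that holds all three has no unique solution for the lens effect, yet the plan promises a lens difference with a confidence interval from exactly that model.

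The ways out do not all answer the same question. Removing carryover keeps the within-subject comparison. Removing sequence and keeping carryover reduces the lens estimate to a comparison of different people in period 1. That gives up the own-control comparison which section 4.2 offers as the reason for choosing a crossover. Because the plan does not say which term goes, the quantity to be reported is not fixed in advance.

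**Working it through.** The plan gives no figure to reproduce here. The check is of rank and estimability, followed by an illustration of what the choice of term does.

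**Inputs.** Two sequences, two periods and two lenses (sections 4.1 and 5.1); the fixed effects listed in section 14.7; 60 completers (section 14.2), used only to scale the illustration.

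**Step 1: code the four cells.** TC is Test/Control and CT is Control/Test. Carryover is zero in period 1 and takes the sign of the preceding lens in period 2.

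| Cell | Sequence s | Period p | Lens t | Carryover c | (s − t)/2 |
|---|---|---|---|---|---|
| TC, period 1 | +1 | −1 | +1 | 0 | 0 |
| TC, period 2 | +1 | +1 | −1 | +1 | +1 |
| CT, period 1 | −1 | −1 | −1 | 0 | 0 |
| CT, period 2 | −1 | +1 | +1 | −1 | −1 |

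The last two columns are identical: c = (s − t)/2 in every cell. With the intercept there are five parameters and the matrix has rank 4.

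**Step 2: what can be estimated.** A contrast is estimable only if adding it as a row leaves the rank unchanged. The intercept and period pass. Sequence, lens and carryover fail. Write S, L and C for the coefficients of s, t and c, so that the Test−Control lens difference is 2L and the carryover difference is 2C. The usual crossover contrast, with weights (0.5, −0.5, −0.5, 0.5) on the cells in table order, has expectation 2L − C. That is the lens difference minus half the carryover difference.

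**Step 3: do other model features help?** The dependency lies in the fixed-effect columns, so the random subject effect, the residual covariance structure and the degrees-of-freedom method do not touch it. The lens contrast also failed with carryover coded as a three-level class and as a 0/1 indicator. In a simulated dataset of 66 subjects with two eyes, three timepoints, age, race and period-2 dropouts, the rank was 9, rising to 10 when the lens contrast was added. Removing either carryover or sequence gave 9 and 9.

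**Step 4: the two repairs give different estimates.**

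- Drop carryover: weights (0.5, −0.5, −0.5, 0.5).
- Drop sequence: weights (1, 0, −1, 0), which is period 1 only.

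Take invented cell means of 5, 3, 3 and 3 degrees in table order. The first repair gives 2.5 − 1.5 − 1.5 + 1.5 = 1.0 degree. The second gives 5 − 3 = 2.0 degrees. Each reduced model has four parameters and fits the four means exactly, so fit cannot decide between them.

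**Step 5: precision.** Assume one value per subject-period, equal sequence groups, common SD σ, and correlation ρ between periods. The documents give no ρ, so a range is shown.

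- Carryover dropped: variance = 2σ²(1 − ρ)/N.
- Sequence dropped: variance = 4σ²/N, whatever ρ is.

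With N = 60 and t(0.975, 58 df) = 2.0017, in SD units:

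| ρ | SE, carryover dropped | Half-width | SE, sequence dropped | Half-width | Ratio |
|---|---|---|---|---|---|
| 0 | √(2/60) = 0.18257 | 0.365 | √(4/60) = 0.2582 | 0.517 | 1.4 |
| 0.5 | √(1/60) = 0.1291 | 0.258 | 0.2582 | 0.517 | 2.0 |
| 0.7 | √(0.6/60) = 0.1000 | 0.200 | 0.2582 | 0.517 | 2.6 |

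**The case against.** The algebra is not in dispute, but there is a fair case on weight.

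- **The output is minor.** No endpoint in the study is tested. For settled orientation, the objective in section 2.1 is to "estimate the mean and standard deviation of the settled toric roation of each study lens", which the descriptive summaries deliver without a model. Section 2.1 names a between-lens mean difference only for visual acuity and CLUE. This stands and limits the importance of the point. It does not remove it, because section 14.7 still commits to the model-based means, difference and intervals.
- **The failure would probably be noticed.** Software that checks estimability should flag the least-squares mean difference as non-estimable. A silent wrong number would require reading coefficients from a solution in which a redundant term had been set to zero. This also stands: the likelier consequence is a forced change of model.
- **A change can be made properly.** Section 14.10 provides that "If for any reason a change is made, the change will be documented in the study report", with a justification. The dependency can be seen from the design alone, and section 5.3 aims to keep the project biostatistician masked until database lock. So a late choice is possible but not inevitable. What remains is that no term is named for removal, and the documentation rule does not supply one.
- **The precision figures are hypothetical.** The cell means are invented and ρ is assumed. The endpoint is computed by eye and at three timepoints, so one value per subject-period is not the planned dataset. The widening arises only if sequence is the term dropped, and nothing in the plan suggests it would be. All of this is correct, and the conclusion rests on the rank result alone.

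**Conclusion.** The concern holds. As written, the settled-rotation model has five fixed-effect parameters for four cell means. The lens least-squares means at a common carryover value, the Test−Control difference and their 95% CIs are therefore not estimable. This follows from the design and needs no assumption about the data.

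The practical size depends on how the model is repaired. If carryover is dropped, the within-subject contrast is recovered, on the assumption of no differential carryover. If sequence is dropped instead, the half-width is 1.4 to 2.6 times as wide for assumed ρ between 0 and 0.7, under the simplifications stated with the calculation.

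The defect is confined to the model-based part of one exploratory endpoint and does not bear on the trial's main conclusion. It should be corrected because a stated analysis cannot deliver its stated output.

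**What to change.** In section 14.7, under Mean Settled Lens Orientation, delete the first-order carryover effect so that the fixed effects are sequence, period and lens type. This treats these terms as the CLUE model does and restores the within-subject contrast.

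Add one sentence saying that the lens difference is estimated on the assumption of no differential carryover, supported by the washout of 7 ± 2 days already in the design. If the sponsor wants to look at carryover, it can be named as a separate sensitivity analysis that states which term it replaces.

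The change should be made before unmasking at database lock. It costs one deleted phrase and one added sentence, with no effect on data collection, visits or sample size.

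### The settled-orientation model (Section 14.7) does not say how the two eyes enter the covariance; the one identifiable reading of the three considered sets the correlation of their Test-Control differences to zero, so the 95% CI may have the wrong width.

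*Combined protocol and SAP*

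**What the plan says.** All of the following is in Section 14.7, Mean Settled Lens Orientation, unless marked otherwise.

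- Response: "Mean settled lens orientation is calculated by eye by averaging across all lens orientation measurements collected at least 15-minutes after lens insertion". That is one value per eye.
- Design (Section 5.1): "The study lenses will be worn bilaterally in a randomized fashion using a 2×2 crossover design with 2 lens types and 2 periods". Both eyes wear the same lens type in a period.
- Fixed effects: "Sequence of lens wear, period, lens type, and first order carryover effect will be included in the model as fixed effects". Race, age and similar baseline variables may be added.
- Random part: "Subject will be included as a random effect".
- Residuals: "Residual errors between measurements within a subject across periods will be modeled using an unstructured (UN) covariance structure".
- Degrees of freedom: "The Kenward and Roger Method will be used for the calculation of denominator degrees of freedom".
- Promised result: an estimate and interval for each lens, and "the point estimate with the two-sided 95% CI for the mean difference".

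The model has no fixed effect for eye, no eye-within-subject effect and no subject-by-period effect. The dimension of the unstructured block is not stated.

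**The concern.** Each subject supplies four values per timepoint: two eyes in each of two periods. The lens effect is estimated from within-eye period differences, so the precision of the lens contrast depends on how strongly the right-eye and left-eye differences are correlated. A shared subject intercept carries correlation between the eyes' levels, but it cancels from every within-eye difference. If nothing else in the model links the eyes, their differences are treated as independent. About 120 eyes from 60 subjects then count as 120 independent units.

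At stake is the width of the 95% interval for the Test-Control difference in settled rotation. It would be too narrow if the eyes' differences are positively correlated. It would be too wide if they are negatively correlated, for example if signed rotation mirrors between eyes.

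**Working it through.** **Inputs from the documents.** One value per eye, bilateral wear and two periods (Sections 14.7 and 5.1). At least 60 completers, or 120 eyes (Section 14.2). Two-sided 95% intervals. The documents give no SD, no interval width and no between-eye correlation for this endpoint, so the plan has no figure of its own to reproduce. I assume that the model is fitted separately at each timepoint, since it has no timepoint term. The correlation r is assumed and shown over a range.

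**Step 1: which readings are identifiable?** Count covariance parameters against the distinct variances and covariances that the reading can produce.

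| Reading | Parameters | Moments | Identifiable? |
|---|---|---|---|
| Subject intercept + 2x2 UN per eye | 1 + 3 = 4 | 4 | yes |
| Subject intercept + 4x4 UN per subject (eye by period) | 1 + 10 = 11 | 10 | no |
| Eyes averaged, subject intercept + 2x2 UN | 1 + 3 = 4 | 3 | no |

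In the first row the four moments are the two period variances, the same-eye covariance across periods, and one common between-eye covariance.

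**Step 2: what the per-eye reading implies.** Let s2 be the subject-intercept variance. Any two values from different eyes have covariance s2, whether in the same period or not. For the period differences d_OD and d_OS:

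Cov(d_OD, d_OS) = s2 - s2 - s2 + s2 = 0.

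**Step 3: effect on the interval.** Let each eye's difference have variance v, with n subjects. Up to a common scale factor, the model takes the variance of the mean difference as v/(2n), while the true value is v(1 + r)/(2n). Hence model SE / true SE = 1/sqrt(1 + r), and coverage = 2*Phi(q/sqrt(1 + r)) - 1. Here q is 1.96 for the normal quantile, or 1.980 for t on 2 x 60 - 2 = 118 df.

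| Assumed r | Model SE / true SE | Coverage, q = 1.96 | Coverage, q = 1.980 |
|---|---|---|---|
| -0.3 | 1.20 | 98.1% | 98.2% |
| 0 | 1.00 | 95.0% | 95.2% |
| 0.3 | 0.88 | 91.4% | 91.8% |
| 0.5 | 0.82 | 89.1% | 89.4% |
| 0.7 | 0.77 | 86.7% | 87.1% |

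The SE ratio does not depend on n. If all of about 66 ITT subjects contribute (132 eyes), only q moves, and only slightly.

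**Step 4: check by REML simulation.** With 60 subjects, an assumed residual SD of 3 and no carryover term, the variance of one eye's difference is 2 x 9 = 18. The true SE is sqrt(18(1 + r)/120).

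| r | True SE | Mean model SE, 2x2 UN per eye | Mean model SE, 4x4 UN per subject |
|---|---|---|---|
| -0.3 | 0.324 | 0.389 | 0.323 |
| 0 | 0.387 | 0.388 | 0.374 |
| 0.3 | 0.442 | 0.386 | 0.433 |
| 0.5 | 0.474 | 0.385 | 0.479 |

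The per-eye model returns the same SE whatever r is; the 4x4 block, fitted without the redundant intercept, follows the truth. The simulated coverages of the per-eye model (98%, 93%, 94% and 88%) come from 150 data sets per row. Their Monte Carlo error is about sqrt(0.95 x 0.05/150) = 1.8 percentage points, so I rely on the formula for coverage.

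**Step 5: can the lens difference be obtained at all?** Order the four cells as Test/Control period 1, period 2, then Control/Test period 1, period 2.

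- Sequence = (0, 0, 1, 1)
- Period = (0, 1, 0, 1)
- Lens = (1, 0, 0, 1)
- Carryover = (0, 1, 0, -1)

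Then 1 - sequence - lens = (0, 1, 0, -1), which is exactly the carryover column. With the intercept there are five columns of rank 4, and the lens difference is not estimable. Without carryover it is.

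**The case against.** The strongest objection is that the plan never states a 2x2 block per eye. The residual sentence names the subject as the unit, and a subject's measurements are four values, so a 4x4 eye-by-period block fits those words. Under it the SE is right. The redundancy with the subject intercept is then a fitting problem: the total covariance, and so the SE of the lens difference, is still determined. The same holds if the eyes are averaged first. This stands. A reader might infer that the plan treats the eyes' differences as independent and that its interval is therefore wrong. The documents do not support that as a statement of fact. They leave the eye-level structure open.

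Other points also stand. Even under the per-eye reading the width is wrong only if r is not zero, and neither its size nor its sign is given. Lens power and axis are chosen from each eye's own refraction (Section 7.2), and rotation is recorded with its direction, so mirror-image behaviour is possible. No hypothesis is tested for any endpoint (Sections 2.3 and 14.4), and the objective for settled orientation in Section 2.1 is the mean and SD of each lens, not their difference.

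These points do not remove the need for a change. The 4x4 reading requires the reader to supply eye as a dimension where the text gives only periods, and then to drop a random effect that the text includes. Either the correlation is left out, or the analyst must alter the written covariance without a prespecified rule.

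**Conclusion.** The concern holds in a limited form. The plan analyses an eye-level response without saying how eye enters the covariance. Of the three readings considered, the only one under which both written terms are identifiable sets the between-eye covariance of the Test-Control differences to zero. Under that reading nominal 95% coverage becomes about 91% at r = 0.3, 89% at r = 0.5 and 98% at r = -0.3, with no error at r = 0. These values of r are assumptions, and the direction of the error is open.

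The carryover term in the same paragraph is the more basic obstacle: with it, the promised interval for the lens difference cannot be obtained. Both matters are minor to moderate, because the endpoint is exploratory and no decision rule depends on it.

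**What to change.** Before database lock, state one covariance structure for the four eye-by-period values. Any of these would do:

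1. One block per subject, either 4x4 UN (10 parameters) or UN(eye) x UN(period) (3 + 3 - 1 = 5), without the separate random subject effect.
2. Random subject, subject-by-period and eye-within-subject effects with a simple residual (4 parameters). Here Cov(d_OD, d_OS) is twice the subject-by-period variance. A variance held at or above zero therefore cannot represent a negative r.
3. The mean of the two eyes per subject and period, with UN across periods (3 parameters) and no random subject effect.

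Because the sign of r is unknown, the 4x4 block or the averaged eyes are the safer choices. The product form allows either sign, but ties the between-eye correlation of the differences to that of the levels.

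Remove first-order carryover from the fixed effects, keeping sequence, period and lens. State also the sign convention for rotation in right and left eyes, and that the model is fitted per timepoint if that is intended.

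The cost is a few sentences in Section 14.7 and no new data. Against the 4 parameters of the per-eye reading, the product form adds one and the 4x4 block six; the other two options add none. The interval may become wider if r is positive.
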